1. The test statistic is the effect regression coefficient from a mixed-effects logistic regression model
2. Alpha = 0.05
3. Power = 90%
4. The proportion consenting to testing in the control group will be 0.85
5. The proportion consenting to testing in the intervention group will be 0.98 (a difference of +0.13 vs the control group).
6. An average of two household contacts will be eligible for HIV testing per household. The intra-class correlation (ICC) will be 0.59.

The total number of households needed is sensitive to the mean cluster size. Under the preceding assumptions, the necessary number of households may range from 152 if the mean number of eligible contacts per households is 2 to 138 if the mean number of contacts per household is 3. The total

number of households needed is also sensitive to the ICC. Sample size estimates assuming a range of possible ICC values, ranging from the value observed during the preliminary research (0.59) to higher values (0.65, 0.70), are not presented here although considered by the study team. Finally, the total number of households needed is sensitive to the baseline (control group) proportion of tests accepted. Sample size estimates assuming three possible baseline testing rates (75%, 80%, and 85%) in control group households have been considered. We will plan an interim blinded power analysis by an external biostatistician to readjust sample size targets as necessary for actual mean cluster size and ICC after enrolling the first 100 households.

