Analysis. In the Aim 2 analysis, our primary outcome is change in perceived HIV-TB stigma after following the first household contact tracing visit; the secondary outcome is uptake of HIV testing; we will descriptively assess linkage to care from both baseline data and intervention households. We will calculate descriptive statistics for participant characteristics, and test associations between characteristics and perceived/attributed household stigma. To test the hypothesis that invitation scripts that apply acceptance-optimized sequencing of oral test offers and prosocial messaging can decrease HIV stigma within households, we will evaluate change in HIV-TB stigma using cluster-adjusted dependent t-tests and fitting multilevel models with clustered standard errors. To test the hypothesis that prosocial messaging and theory-informed sequencing of HIV test offers can increase test uptake, we will compare testing uptake among the intervention households and pre-implementation households using cluster-adjusted chi-squared tests of proportion and by fitting multilevel logistic regression models. All hypothesis tests will be carried out at alpha of 0.05, corrected for multiple tests as appropriate. We will report household ICC for stigma as well as test uptake.

5. Genetic Testing N/A

6. **Subject Population:** Provide a detailed description of the types of human subjects who will be recruited into this study.

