In the Aim 2 analysis, we will calculate and compare uptake across each of the trial arms using an intention-to-treat analysis. We will also consider a per protocol analysis and model adjusted for imbalances in baseline confounders as secondary analyses. To test the hypothesis that a norming intervention can increase test uptake, we will compare testing uptake among the intervention households and control households using cluster-adjusted chi-squared tests of proportion and by fitting mixed effects logistic regression models with two levels (household, contact.) To test the hypothesis that invitation scripts that apply acceptance-optimized sequencing of oral test offers and prosocial messaging can decrease HIV stigma within households, we will evaluate change in HIV-TB stigma using cluster-adjusted dependent t-tests and fitting multilevel models with clustered standard errors. We will conduct a causal mediation analysis to determine to what degree the effects of the intervention on stigma explain the improvement in test uptake using observed-variable structural equation modeling. All hypothesis tests will be carried out at alpha of 0.05, corrected for multiple tests as appropriate. We will report household ICC for stigma as well as test uptake and will consider a household ICC of >0.2 a sufficient level of clustering necessitating adjustment.

SECTION II: RESEARCH INVOLVING DRUGS, BIOLOGICS, RADIOTRACERS, PLACEBOS AND DEVICES

If this section (or one of its parts, A or B) is not applicable, check off N/A and delete the rest of the section.

A. RADIOTRACERS N/A

B. DRUGS/BIOLOGICS N/A

B. DEVICES N/A

SECTION III: RECRUITMENT/CONSENT AND ASSENT PROCEDURES**1. Targeted Enrollment: Give the number of subjects:**

- a. Targeted for enrollment at Yale for this protocol: 0
- b. If this is a multi-site study, give the total number of subjects targeted across all sites:
 - 40 to 60 individuals drawn from 20 households (Aim 1)
 - Approximately 8 to 15 lay health workers with experience carrying out TB contact investigation
 - Approximately 60-100 health workers participating in HIV and TB care services during the COVID-19 pandemic
 - Approximately 152 index patients and their approximately 304 household contacts (Aim 2)

2. Indicate recruitment methods below. Attach copies of any recruitment materials that will be used.

 Flyers	 Internet/web postings	 Radio

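### The plan states no intervention-versus-control comparison for the primary stigma outcome: paired t-tests cannot provide one, and the multilevel models have no stated arm or baseline term

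*Combined protocol and SAP*

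**What the plan says.** The Aim 2 Analysis paragraph (Section I, 4. Research Plan) states that "our primary outcome is change in perceived HIV-TB stigma after following the first household contact tracing visit". The Aim 2 text in the Statement of Purpose calls HIV and TB stigma co-primary. The test of the stigma hypothesis is given in the same words in the Analysis paragraph and in Section I, 13. Statistical Considerations: "we will evaluate change in HIV-TB stigma using cluster-adjusted dependent t-tests and fitting multilevel models with clustered standard errors". Neither place names a comparator for stigma, and neither ranks the two methods.

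Comparators are named for uptake. Section 13 plans an intention-to-treat comparison of uptake between the trial arms and says "we will compare testing uptake among the intervention households and control households using cluster-adjusted chi-squared tests of proportion". The Analysis paragraph names a different comparator, also for uptake: it will "compare testing uptake among the intervention households and pre-implementation households". That paragraph does not mention the control arm.

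The nearest the plan comes to an arm effect on stigma is the mediation analysis in Section 13, which asks "to what degree the effects of the intervention on stigma explain the improvement in test uptake".

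**The concern.** A dependent t-test on start- and end-of-visit scores asks whether the mean within-person change is zero. It does not use the randomised control group. The multilevel models could use it, but the plan does not say what they contain.

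This matters because of how stigma is measured. The short scales are given at the beginning and end of the same home visit, in both arms. Health workers in both arms are trained to deliver oral testing with HIV education and counselling (CHW Training), and both arms are offered a test in between. Scores could fall in both arms for reasons unrelated to sequencing, prosocial script or opt-out framing.

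As written, such a shared fall could be reported as support for the stigma hypothesis. Measuring change in control households does not prevent this: finding a significant fall in one arm and not in the other is not a test of the difference between arms. Because neither method is primary, the analyst could also decide which to emphasise after seeing the results.

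**Working it through.** **The plan's own figure.** The only power calculation (Sample Size) concerns uptake: 0.85 versus 0.98, alpha 0.05, power 90%, two contacts per household, and "The intra-class correlation (ICC) will be 0.59". With a pooled-variance, two-sided two-proportion formula:

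- n per arm = [1.96·√(2·0.915·0.085) + 1.2816·√(0.85·0.15 + 0.98·0.02)]² / 0.13² = 94.6, so 95 contacts.
- Design effect = 1 + (2 − 1)·0.59 = 1.59. Households per arm = 95·1.59/2 = 75.5, so 76, or 152 in total. This matches.
- With three contacts: 95·2.18/3 = 69.03, so 70 per arm, or 140 in total, against the stated 138.

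The uptake figure is sound. No corresponding figure exists for stigma.

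**Inputs for the stigma illustration.** From the plan: 76 households × 2 contacts = 152 contacts per arm. The documents give no stigma SD, pre-post correlation r, stigma ICC or expected drift, so these are assumptions:

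- score SD = 1 at each time;
- r = 0.5 to 0.7;
- ICC from 0.2 to 0.59. The lower value is the Section 13 threshold (the plan "will consider a household ICC of >0.2 a sufficient level of clustering necessitating adjustment"); the upper is the uptake value;
- the same fall d in both arms, with a true intervention effect of zero.

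**Formulas.** The plan does not say on whom the paired test is run, so three readings are shown.

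- Standard error (SE) of mean change in one arm = √[2(1 − r)(1 + ICC)/152]. This is 0.0688 at r = 0.7, ICC = 0.2, and 0.1023 at r = 0.5, ICC = 0.59.
- (a) Intervention arm alone, significant fall: p = Φ(d/SE − 1.96).
- (b) Both arms pooled: replace SE by SE/√2.
- (c) Significant fall in intervention but not in control: p(1 − p).

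At d = 0.2: Φ(0.2/0.0688 − 1.96) = 0.828 and Φ(0.2/0.1023 − 1.96) = 0.498. The other two corners give 0.614 and 0.714.

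| Shared fall, alpha | (a) intervention arm | (b) pooled | (c) intervention yes, control no |
|---|---|---|---|
| 0 SD, 0.05 | 2.5% | 2.5% | 2.4% |
| 0.1 SD, 0.05 | 16%–31% | 28%–54% | 14%–21% |
| 0.2 SD, 0.05 | 50%–83% | 79%–98% | 14%–25% |
| 0.2 SD, 0.025 per scale | 39%–75% | 70%–97% | 19%–25% |

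A between-arm test at alpha 0.05 is significant in 5% of trials, 2.5% in the favourable direction, whatever the shared fall.

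**Check by simulation** (0.2 SD fall, 4000 trials at each of the four corners, alpha 0.05): (a) 49%–81%, (b) 79%–98%, (c) 15%–25%. A baseline-adjusted between-arm test rejected in 4.7%–5.1% (2.0%–2.8% favourable) and a between-arm change-score test in 4.6%–5.2%.

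**What a between-arm analysis can detect with 152 households.** The 90%-power detectable difference is (z + 1.2816)·√[2(1 + ICC)/152]·k, with z = 1.96 at alpha 0.05. For baseline adjustment k = √(1 − r²); for change scores k = √[2(1 − r)].

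- Baseline-adjusted: 0.29–0.41 SD at alpha 0.05; 0.32–0.44 SD at alpha 0.025 per scale.
- Change score: 0.32–0.47 SD at alpha 0.05.
- Variance ratio, adjusted to change score: (1 − r²)/[2(1 − r)] = (1 + r)/2, or 75% to 85%.

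**The case against.** The strongest reply is that the comparison is obvious. Aim 2 evaluates the intervention's effect on stigma in a household-randomised trial, the scales are collected in both arms, and the scripts named in the hypothesis belong to the intervention arm. The natural exposure in a multilevel model is therefore arm, and the mediation analysis needs a path from arm to stigma. This stands as evidence of intent: the investigators clearly mean to compare arms. It does not say which analysis does so, with which terms, or that it takes precedence over the paired test.

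The plan also commits to both methods, so the analyst cannot simply discard one. That is fair; the freedom left is which result to lead with and how to build the model.

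The figures depend on an assumed drift. This stands too: with no shared fall the paired test is not inflated. Readings (b) and (c) are not described in the plan, and the 0.59 ICC belongs to a binary outcome. The percentages show how the error would behave and do not predict it. The defect does not depend on them.

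Baseline adjustment is one valid choice among several, and this is a pilot. Both points are true. Even so, the plan promises hypothesis tests at alpha 0.05, and its results are meant to inform a future randomised study.

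**Conclusion.** The concern holds and should be fixed. The only stated test of the primary stigma hypothesis pairs a method that cannot use the randomised control with a model whose terms are not given, and neither is primary. The secondary outcome, uptake, has the between-arm, intention-to-treat wording that the primary outcome lacks. The gap is in specification; the design itself is sound and already collects what is needed.

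The size depends on how far scores fall in both arms alike. For a shared fall of 0.2 SD and no intervention effect, a paired test in the intervention arm would be significant in 50% to 83% of trials; for 0.1 SD, 16% to 31%; for none, the nominal 2.5% in the favourable direction. These ranges rest on the assumed correlation and ICC.

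**What to change.** In the Aim 2 Analysis paragraph and in Section 13, replace the stigma sentence with:

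> For each of the HIV and TB stigma scales, the primary analysis is an intention-to-treat linear mixed model of the end-of-visit score on arm and the contact's start-of-visit score, with a household random intercept. We will report the adjusted intervention-minus-control difference with its 95% CI. Dependent t-tests will be reported within each arm as description only.

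This follows the co-primary wording in the Statement of Purpose. If a single combined score is meant, the same model applies to that score and the plan should say so. A between-arm change-score model or an arm-by-time model would also be valid. Baseline adjustment is proposed because, under the assumptions above, it has 75% to 85% of the variance of the change-score comparison.

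Optionally, add to Sample Size the stigma difference detectable with 152 households as an assumption-based range: 0.29–0.41 SD, or 0.32–0.44 SD if alpha is split between the two scales.

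The cost is a wording change in two paragraphs, with no extra data, visits or participants.

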Analysis. After professionally transcribing and importing interviews into a qualitative data analysis application, we will carry out a grounded-theory analysis. Two coders will independently read transcripts to identify themes, produce a codebook, and apply codes. We will assess the acceptability of acceptance-optimized sequencing of HIV test offers to clients and LHWs by inductive analysis of responses to the prototype sequence, and acceptability of inviting the first tester to share their choice to test (but not results) by inductive analysis of themes relevant to sharing of test decision. For both acceptability outcomes, we will calculate the proportions who affirmatively describe each element of the intervention as acceptable in principle and estimate the extent to which this is correlated within households. We will qualitatively assess change in perceived stigma associated with learning that the first household member chose to test as well as change in perceived stigma associated with provider-initiated invitation scripts that apply prosocial messaging by analyzing the decision narratives. Because the aim of the interviews is to iteratively refine the intervention, the prototype will evolve over the course of data collection, and we will not conduct formal statistical tests.

Parallel follow-up survey and short-form interview, and validation studies: We will also conduct two sub-studies nested within Aim 1 participants. These studies will help to adapt and validate a variation of the Van Rie HIV- and TB-related stigma scales to 1) improve their legibility to TB patients and their close contacts, 2) more effectively target these scales to distinguish between the presence of perceived stigma from the household versus perceived stigma from the community at large. We will make adjustments to the scales and then conduct short follow up surveys and/or interviews with Aim 1 participants to compare HIV and TB stigma scale answers with those provided at baseline. We will re-contact these participants via telephone, through a secondary household visit or through an invitation to an acceptable site such as the health facility or the U-TIRC study offices.

Procedures for Aim 2:

Routine data collection. We will collect routine household contact investigation and home HIV testing uptake data from the contact registers of the 4 participating TB units.

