CHW Training We will carry out a participatory training with the study CHWs. First, CHWs will meet as a group to discuss study aims, the trial design, and the importance of study controls. Next, CHWs will be split into Clinic Based CHWs, Intervention CHWs and CHWs doing Routine Contact Investigation. Each group will separately review and role play their assigned procedures. Clinic Based CHWs will be trained to provide TB education and counselling, index patient enrolment, and randomization procedures. Intervention CHWs will be trained to deliver the social-behavioural intervention finalized in Aim 1. Standard of Care CHWs will be trained to deliver a standard offer of opt-in HIV testing. Both Standard of Care CHWs and Intervention CHWs will be trained in the use and delivery of oral HIV testing kits including the delivery of HIV education and counselling.

Household-Randomized controlled trial. LHWs attached to 2 TB units in Kampala Uganda will identify, invite, consent, and enroll approximately 152 consecutive, eligible index patients for household contact investigation for TB. We anticipate these households containing approximately 304 household contacts with approximately 1:1 randomization (half in each study arm). Upon index patient consent, we will collect demographic information from each index patient at enrollment, including age, gender, occupation (if applicable), income (if applicable), education in years, and household composition,

including number, age, gender, relationship to, and perceived influence of self-reported household contacts. After study enrolment and collection of index patient demographic data, a CHW will work with the index patient and, if available, treatment supporter to schedule the home visit. Households will be randomly assigned to one of the two CHW teams to receive the intervention or standard of care. The study CHW will note the self-reported number of household contacts aged 15 or older and requisition the appropriate number of HIV test kits based on the number of reported contacts, adding two extra kits for extra margin.

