LHWs will carry out home visits in pairs or with 3 LHWs dependent on the needs of that household. A LHW employed by the clinics will provide routine contact investigation services and a trained study LHW will collect research data and deliver the intervention for those randomized to the intervention arm of the study. While the LHW carries out standard contact investigation screening, the study LHW will administer a short HIV-TB stigma scale individually to all consenting adult members of the household in both arms. The research LHW will follow the assigned script based on randomization allocation to identify household members who are eligible and invite them to test for HIV, recording time-stamped offers, test decisions, and test results. The research LHW will collect household- and individual-level demographic, socioeconomic data, stigma scales, measures of household stability, including household tenure in years as well as relationship to and perceived influence of household members and clinical data using a structured survey.

Procedures for all households: Upon arrival, the CHWs will enroll all eligible, consenting household contacts in the study. But before doing this, at the start, CHWs will introduce themselves and ask for introduction of contacts. At this time the master list of all the contacts will be created.

- They will introduce the reason for their visit and the services they will offer (TBCI, oral HIV testing) using the introductory script for either Intervention or Routine Contact Investigation households, depending on the household assignment.
- For the intervention arm, one CHW will take the index case to a private area to ask the influence questions using the paper form (master list) as a key. After completing this exercise, the CHW will then embark conducting household contact screening interviews followed by HIV testing and any other study related activities. All data will be collected via CommCare.
- Meanwhile, the other CHW will be conducting routine TB contact investigation activities and any other clinical procedures in household TB contact investigation. Details of these procedures are found below:

a) Index case influence questions

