Randomization: For aim 2 of the study, variable block randomization will be done at the level of the household and will be performed at the time of household enrollment. Block sizes will have a minimum of 2, a maximum of 6. We will utilize study randomizer, an online randomization tool with concealed randomization. When a CHW has deemed an index patient and their household to be eligible for the study, and after the index patient or their guardian has provided verbal informed consent, the CHW will place a phone call to the study coordinator. The study coordinator will then enroll the household using the study randomizer tool and let the CHW know the study allocation. The CHW will then fill in the appropriate allocation, along with the randomization ID, and contact the appropriate CHW team for the household visit.

Households randomized to intervention group will be offered oral testing with the social-behavioral intervention. Households randomized to the standard of care group will be offered oral testing without any social-behavioral intervention. CHWs will operate in teams that are always assigned to the same arm of the study. There will be three teams of CHWs in total: one intervention group, one standard of care group, and one clinic-based group that will always be in charge of initial enrollment of index patients and recording any clinic follow up by individuals in either arm of the study.

Integrated intervention. In Intervention Households only, the CHW will present the opportunity to test using the script and procedures described in the next section (“Specification of intervention components”). This script communicates that the individual is completely free to opt out of testing, but that testing is the norm. We will use “Opt-Out” testing language along with language letting them know that they can decline.

If the household contact decides to opt out of HIV testing, the CHW will carry out a survey. These questions will take approximately the same amount of time as HIV testing and counselling procedures (~20 to 30 minutes) in order to blind other household members from the testing decision of that household contact. Contact decisions to test or not to test as well as test results will be recorded in CommCare.

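### The protocol names two different comparators for Aim 2 HIV test uptake: undefined pre-implementation households in the Research Plan, control households in Statistical Considerations

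*Combined protocol and SAP*

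**What the plan says.** Two current sections describe the Aim 2 test of HIV test uptake.

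- **Section I, item 4, Research Plan, Aim 2 Analysis paragraph:** "we will compare testing uptake among the intervention households and pre-implementation households using cluster-adjusted chi-squared tests of proportion", together with multilevel logistic models. The same paragraph makes perceived stigma the primary outcome and uptake the secondary one. It describes linkage to care from baseline data and intervention households.
- **Section I, item 13, Statistical Considerations:** "we will compare testing uptake among the intervention households and control households using cluster-adjusted chi-squared tests of proportion", together with two-level mixed-effects logistic models. It opens the Aim 2 analysis with "we will calculate and compare uptake across each of the trial arms using an intention-to-treat analysis".

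The term pre-implementation households occurs only in the first of these. No source, period, eligibility rule, number or uptake rate is attached to it. The nearest candidate is the routine data collection item under Procedures for Aim 2: "We will collect routine household contact investigation and home HIV testing uptake data from the contact registers of the 4 participating TB units". That item does not call the data pre-implementation, gives no dates and does not name them as a comparator. The trial itself recruits from fewer sites: "LHWs attached to 2 TB units in Kampala Uganda will identify, invite, consent, and enroll approximately 152 consecutive, eligible index patients".

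**The concern.** The two sentences state the same kind of hypothesis, name the same chi-squared test and differ in the comparator. One contrast is randomised and concurrent. The other is neither, and cannot be carried out as written because its comparison group is not identified.

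The choice affects what the result means. Both arms receive the oral test: "Households randomized to the standard of care group will be offered oral testing without any social-behavioral intervention". The randomised contrast therefore isolates the social-behavioural package. A contrast with earlier households could also pick up calendar time, study staff and the effect of being enrolled in a trial. It could pick up the oral kit if that was not offered earlier, and a different mix of sites if the four-unit registers were the source. Any of these could be credited to the script and the sequencing.

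With both rules in the protocol, the comparator could also be settled after the data are seen, and a reader could not tell from the protocol which was intended.

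**Working it through.** **1. Which comparator does the rest of the plan support?**

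- Aim 2 in the Statement of Purpose assigns households at random to two arms.
- The Randomization paragraph describes concealed, household-level allocation to intervention or standard of care.
- Under the Household-Randomized controlled trial heading, the research health worker follows the script for the assigned arm, "recording time-stamped offers, test decisions, and test results", so uptake is recorded in the control arm.
- The Sample Size paragraph powers a two-arm household-randomised trial on a control proportion and an intervention proportion.

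All of these point to the randomised control arm.

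**2. Does the stated sample size come from the control-arm contrast?**

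Inputs from the Sample Size paragraph: alpha 0.05 (sidedness not stated; two-sided assumed), power 90%, control 0.85, intervention 0.98, ICC 0.59, mean of 2 eligible contacts per household, or 3 as the alternative. The average of the two proportions is 0.915.

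Contacts per arm before clustering:

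n = [1.960 × √(2 × 0.915 × 0.085) + 1.2816 × √(0.85 × 0.15 + 0.98 × 0.02)]² / 0.13²
= (0.7730 + 0.4915)² / 0.0169 = 94.6

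Design effect = 1 + (m − 1) × 0.59:

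| Mean contacts m | Design effect | Contacts per arm | Households per arm | Total households | Plan |
|---|---|---|---|---|---|
| 2 | 1.59 | 150.4 | 75.2, rounded up to 76 | 152 | 152 |
| 3 | 2.18 | 206.3 | 68.8, rounded up to 69 | 138 | 138 |

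Both agree with the plan: "the necessary number of households may range from 152 if the mean number of eligible contacts per households is 2 to 138". (Rounding 94.6 up to 95 before applying the design effect gives 140 instead of 138 for m = 3; the difference is rounding only.) No corresponding calculation is possible for pre-implementation households, because no number, rate or ICC is given for them.

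**3. What could the other comparator do?**

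The documents give no pre-implementation uptake, so this is an illustration under assumptions. Suppose the intervention has no effect and uptake is 85% in both randomised arms.

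- Apparent gain = 0.85 − assumed pre-implementation uptake.
- The last column is the chance of a significant result favouring the intervention. It uses the same normal-approximation test and assumes that both groups have the trial's effective size per arm, 152 contacts / 1.59 = 95.6.

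| Assumed pre-implementation uptake | Apparent gain (points) | Chance of a significant result favouring the intervention |
|---|---|---|
| 85% | 0 | 2.5% |
| 80% | 5 | 15% |
| 75% | 10 | 41% |
| 72% | 13 | 59% |

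The rates 75%, 80% and 85% are those the Sample Size paragraph considered for the control group; they are borrowed here only to span a range. The 72% row is where the spurious gain equals the planned effect (0.85 − 0.13). Background reports 53% uptake among household contacts of TB patients. That would give 32 points, but nothing ties the figure to these households, so it is an outer limit and not an estimate.

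**The case against.** The strongest reply is that the phrase stands alone. Every other part of the protocol uses the concurrent control, and Statistical Considerations gives the fuller account: intention to treat first, with per-protocol and adjusted analyses as secondary. On this view the Research Plan wording is a drafting slip or an unlabelled extra comparison, and a non-randomised analysis is unlikely. Neither section says its comparison is the only one. Uptake is a secondary outcome of a pilot, and the bias figures rest on assumed rates.

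Much of this stands. The correct contrast is prespecified in item 13, which limits the severity. The comparison may have been meant as an addition. The bias table shows what could happen, not what would.

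It does not remove the contradiction. The Research Plan paragraph is the one that labels the outcomes, and it presents the pre-implementation contrast as the test of the uptake hypothesis at alpha 0.05, not as supplementary. It never mentions the control arm for uptake. The sample size also rests on uptake, despite its secondary label.

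Two side points carry less weight. The mismatch between four and two TB units matters here only if the registers are the intended source. The reference to baseline data for linkage is ambiguous, not wrong: the Sample Size paragraph uses baseline to mean the control group, and linkage is descriptive only.

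**Conclusion.** The concern holds. Two current sections give different comparators for the same outcome, one of them is undefined, and nothing ranks them. The text alone establishes this; no assumption is needed. The plan's 152 and 138 households reproduce from the control-arm inputs (two-sided alpha assumed), so the sample size supports item 13.

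The size of any bias cannot be known from the documents. With 85% uptake in both arms and no effect, the illustrated range is 0 to 10 points for pre-implementation uptake between 85% and 75%, and the spurious gain equals or exceeds the planned 13 points at 72% or below. This should be fixed, but it is not fatal, because the randomised intention-to-treat comparison is already in the plan.

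**What to change.** In the Aim 2 Analysis paragraph of the Research Plan:

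- Replace the pre-implementation comparator with households randomised to the control arm, analysed by intention to treat, so that it agrees with Statistical Considerations.
- If a pre-implementation comparison is wanted, for example from the routine registers, define its source, TB units, dates and eligibility, and label it descriptive only.
- State that linkage to care is described by randomised arm, in place of the reference to baseline data.

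The cost is a wording amendment. The plan already records test decisions in the control arm, and the sample size already assumes that contrast, so neither data collection nor the number of households changes.
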